Trained research staff will obtain sober, written informed consent prior to participation in the screening process (using the Screening Consent form). An investigator or study coordinator will obtain sober, written study consent prior to research participation (with the Main Study Consent form). Participants will be required to have a negative alcohol breathalyzer test prior to signing consent and not be stumbling, nodding or appearing intoxicated. Volunteers who have a positive breathalyzer test or appear intoxicated will be asked to return at a later time when they are sober. Volunteers must be fluent in English and are required to take a literacy test to determine reading level. Volunteers will meet with the investigator, physician or the study coordinator on an outpatient basis prior to admission in order to review all experimental procedures and allow the volunteer to ask any questions regarding the protocol prior to signing the study Informed Consent form. There is no time limit on this process. The investigator will also inform the volunteer that this is not a treatment program and that signing the consent form does not obligate them to participate. Each volunteer will receive a copy of the signed consent forms.

Participants may also be consented via Zoom. All consenting procedures will be identical to an in-person consent, except the PI will be present via Zoom (instead of the same room). The participant will be screened by in-person research staff (e.g., participants provided photo ID, negative breathalyzer samples and protocol-appropriate urine samples; staff confirmed participants were not intoxicated). Research staff will provide the consent form to the participant, which will be verified on camera by the PI. This process allows for a thorough discussion and exchange of information with the participant, a method to ensure the participant's identity, and documentation of the consent itself.

Subjects may ask study personnel questions about the study or make complaints at any time. All staff will be aware to contact Drs. [name], [name] or [name] about any subject concern or complaint as it arises. Phone numbers for the study PI, as well as the Office of Research Integrity are included in the consent form. It is expected that providing a phone number and contact information for the PI may offer a safe, confidential and reliable channel for participants to express problems, concerns or questions and obtain study information.

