Due to the double-dummy design of this study, both vaporized marijuana and a cocktail will administered during each session. The vaporized dose will contain an active dose of marijuana or placebo. Cocktails will be comprised of an oral solution containing alcohol (0.8 g/kg, mixed with juice) or placebo (a very small amount of alcohol to mask the placebo). Active marijuana and active alcohol doses will not be administered in combination.

Healthy volunteers will participate in a total of 5 experimental sessions. During each session, the doses will be administered under double-blind conditions, and data will be collected for approximately 8 hours post-dose. Each session is designed to collect an array of multi-dimensional data, including subjective effect questionnaires of positive and negative mood, observer ratings, physiological measures, driving simulator performance and cognitive tasks (see below under Outpatient Research Procedures for further detail).

Attachments

Attach Type	File Name
StudyDesign	Screening Packet.pdf

Subject Recruitment Methods & Advertising

Describe how the study team will identify and recruit subjects. Please consider the following items and provide additional information as needed so that the IRB can follow each step of the recruitment process.

- How will the study team identify potential participants?
- Who will first contact the potential subjects, and how?
- Will you use advertisements? If so, how will you distribute those?
- How and where will the research team meet with potential participants?
- If applicable, describe proposed outreach programs for recruiting women, minorities, or disparate populations.
- How you will minimize undue influence in recruitment?
- Attach copies of all recruiting and advertising materials (emails, verbal scripts, flyers, posts, messages, etc.).

For additional information on recruiting and advertising:

- [IRB Application Instructions - Advertisements](#)
- [PI Guide to Identification and Recruitment of Human Subjects for Research](#)

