The content and flow of experimental sessions are designed to capture the time-action curves for the test agents at the selected doses (peak subjective effects of high potency marijuana ~ 15 mins – 3 hrs (Haney et al., 2016; Hunault et al., 2014; Ramaekers et al., 2006) alcohol (0.8 g/kg) ~ 15 min – 3 hrs (Kirkpatrick & de Wit, 2013)). The oral alcohol solution will be administered 15 minutes prior to smoked marijuana; however, only one agent will be active (i.e., active alcohol + placebo marijuana; active marijuana + placebo drink). Participants will vaporize marijuana (approx. 166 mg total weight). Driving simulation will be tested at six time points during each test session at baseline, 15 min and 1, 2, 4, and 6 hr post-marijuana dose. This will allow us to examine the driving ability 1) immediately after smoking (15 min), 2) during peak subjective ratings of feeling high (15 mins-2 hrs), (Hunault et al., 2014; Ramaekers et al., 2006) and 3) after subjective intoxication has subsided, but while sedation is expected to remain elevated (6 hrs). (Hunault et al., 2014)

Participants are required 1) to successfully complete a field sobriety test, 2) have a BAC = 0.02, and 3) report no acute intoxication in order to be discharged from the session. Free round-trip transportation will be provided for subject safety (e.g., taxi). Participants are not permitted to transport themselves home.

Study Drug

All drug doses will be stored at the UK Robert Straus Research Facility under secure conditions specially equipped for Schedule I drug storage. Doses will be blinded by the University of Kentucky (UK) Investigational Pharmacy licensed pharmacists (Drs. [name], [name]). Marijuana will be obtained through the NIDA drug supply. Each vaporized dose will contain approximately 166 mg of plant material. Research Triangle Institute (RTI) will provide chemical analysis reports of marijuana cannabinoid concentrations with each lot of marijuana, which will be reviewed by the PI for consistency. A Volcano brand vaporizer will be used to deliver the doses. This model has been used in several studies (e.g., Spindle et al., 2018; JAMA) and is more efficient delivery system than a marijuana cigarette (drug is lost through combustion and side stream smoke; a vaporizer is a closed system that eliminates these

concerns). Alcohol doses (USP-grade ethanol, juice mixer) and placebo drinks (juice with 1% alcohol) will be prepared by the pharmacists.

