The oral solution (e.g., ~16 oz. drink [450 mL/70 kg]) will contain alcohol (0.8 g/kg) or placebo. Placebo is comprised of juice with a very small amount of alcohol (~3mL or approx. 1% alcohol) floated on top of the drink which produces a scent of alcohol, but does not increase breath alcohol levels. Female participants will receive an alcohol dose that is 15% less than the dose administered to men. This allows for comparable breath alcohol concentrations in men and women (as it helps account for differences in body fat and body water). The alcohol solution will be split into three aliquots contained in an opaque covered cup with a straw. Participants will be asked to complete the alcohol solution in 15 minutes (e.g., approx. 5 minutes per aliquot). The active alcohol solution will produce a breath alcohol level of approximately 0.08 within approximately half hour of administration (Kirkpatrick & de Wit, 2013).

Outpatient Methods

For each experimental session, participants will arrive at the laboratory in the morning having abstained from alcohol for 24 hrs, cigarettes and caffeine for 8 hrs, and having fasted (water permitted, no food) since waking. Session will be conducted if urine samples test negative for drugs of abuse (aside from THC) and pregnancy in females; breath samples must test negative (0.000 BAC) for alcohol and cigarette/marijuana smoking abstinence will be confirmed (below approximately 15 PPM CO). After CO is confirmed to be below the cut-off, cigarette smoking and coffee (with standardized caffeine content) will be permitted 1 hr before dosing and after session (we have previously used similar models for marijuana and alcohol studies. A standardized breakfast will be provided approximately 1 hr prior to dose administration.

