We have developed driving scenario courses with comparable variables and construct characteristics for use in repeated testing designs. These driving scenarios are approximately 10 minutes in length and include various highway and city driving courses. We are familiar with the consensus recommendations from the International Council on Alcohol, Drugs & Traffic Safety's (ICADTS) for behavioral outcomes in drugged driving studies and will focus on those outcomes most commonly evaluated in driving simulator studies, for example, lateral position variability (i.e., a marker of lane deviation and tactical measures (deceleration maneuvering in response to an obstacle or yellow light). However, other variables will be explored.

Data will be collected for approximately 8 hours post-dose (e.g., relative to marijuana administration) and we expect total session participation time will be approximately 9 hours. A field sobriety test will be completed in the presence of an investigator or senior staff member before participants will be released to go home. If the participant exhibits signs of impairment, they will be retained at the laboratory and re-assessed every 20 minutes (and paid a rate of \$10/hr for this extra time). In our experience, the effects of marijuana are minimal at 8 hours post-dose and breath alcohol levels should be 0.00 – 0.02 at this time. Participants will not be permitted to transport themselves home under any circumstance. We will provide transportation (for example: taxi, Uber, similar car service). Alternatively, a participant can arrange for a friend/family member to provide transportation if they choose. We will also advise participants not to use drugs or alcohol on the day of session (either prior to or after the session has been completed) and not to drive a car or operate machinery for the remainder of the day. We have successfully administered smoked marijuana and alcohol on an outpatient basis using similar methods (Protocols #15-0976-F3R, #14-0769-F3R, #11-0100-F6A).

Sessions in which active drug doses are administered will be followed by at least one wash-out day prior to the next session (e.g., minimum of 48 hours between doses).

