Urine will be collected prior to each session and will be tested for drugs of abuse. Participants must provide a sample that is negative for all drugs of abuse (except THC) prior to each session. Women's samples will also be tested for pregnancy prior to each session to insure that pregnant women do not continue study participation. Pregnant women will be referred to drug abuse treatment and appropriate prenatal care services.

Two to four weeks after study completion, we will schedule a follow-up visit with each participant to determine his/her health status and drug and alcohol use.

Attachments

Data Collection & Research Materials

In this section, please provide the following:

- Describe all sources or methods for obtaining research materials about or from living individuals (such as specimens, records, surveys, interviews, participant observation, etc.), and explain why this information is needed to conduct the study.
- For each source or method described, please list or attach all data to be collected (such as genetic information, interview scripts, survey tools, data collection forms for existing data, etc.).
- If you will conduct a record or chart review, list the beginning and end dates of the records you will view.

Outcome measures for this study will include physiological measures (such as heart rate, blood pressure, oxygen saturation, respiratory rate, and body temperature), performance on subject-rated questionnaires (such as visual analog questionnaires, opiate adjective ratings, Addiction Research Center Inventory, street value questionnaire, and Pharmacological Class Questionnaire), observer ratings, psychomotor/cognitive tasks (such as the Digit Symbol Substitution Task, Trails Making Task), ocular assessments (such as the Maddox Wing) and driving simulator tasks.

Attachments

Resources

Describe the availability of the resources and adequacy of the facilities that you will use to perform the research. Such resources may include:

- Staffing and personnel, in terms of availability, number, expertise, and experience;
- Computer or other technological resources, mobile or otherwise, required or created during the conduct of the research;
- Psychological, social, or medical services, including equipment needed to protect subjects, medical monitoring, ancillary care, or counseling or social support services that may be required because of research participation;

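### No required, checked cannabis abstinence at session start: recent non-smoked use without obvious signs would pass every stated start criterion

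*Protocol*

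**What the plan says.** All references are to the Protocol.

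- **Required abstinence (Research Procedures, Outpatient Methods).** Participants arrive after 24 h without alcohol and 8 h without cigarettes and caffeine, "having fasted (water permitted, no food) since waking". Cannabis has no interval in this list.
- **Conditions for starting (same section).** Urine must be negative for drugs other than THC, and for pregnancy in women. Breath alcohol must be 0.000. For smoking, "cigarette/marijuana smoking abstinence will be confirmed (below approximately 15 PPM CO"). The THC exemption is stated again later: "Participants must provide a sample that is negative for all drugs of abuse (except THC) prior to each session".
- **Session-day instruction (same section).** Staff will "advise participants not to use drugs or alcohol on the day of session (either prior to or after the session has been completed"). No verification or consequence is attached.
- **Who is enrolled (Study Population).** Inclusion criterion 2 accepts a history of either vaporized or smoked use, and criterion 3 requires urine that is positive for cannabinoids.
- **Sobriety rules at other points.** At consent: "Volunteers who have a positive breathalyzer test or appear intoxicated will be asked to return at a later time when they are sober" (Informed Consent Process). At the end of a session, participants must pass a field sobriety test and "report no acute intoxication in order to be discharged from the session" (Research Procedures, General Methods).
- **Dosing hold (Data and Safety Monitoring).** Study drug is withheld from anyone with contraindicating signs or symptoms. The examples given are out-of-range heart rate or blood pressure and serious side effects.

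The SAP has no rule to flag or exclude a session for recent cannabis use.

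**The concern.** Cannabis is the main study drug and everyone enrolled uses it. Alcohol abstinence before a session is both required and verified. Cannabis abstinence is verified only through a marker described in terms of smoking, and the broader instruction is left as advice. A participant who vaporized that morning and looks well could therefore be dosed without breaching any stated start criterion.

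What is at stake is participant safety. The session may deliver up to 30 mg THC, or alcohol at 0.8 g/kg (15% less in women), on top of an unrecorded earlier exposure. The likely consequence is unplanned additional impairment in the laboratory.

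**Working it through.** The protocol states no figure for this point, so the check is a reading of the rules against one case, plus simple timing.

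**1. Each start condition against recent vaporized use with no obvious signs**

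| Start condition | Would it stop the session? |
|---|---|
| Urine drug screen | No. THC is exempt, and a cannabinoid-positive sample is an entry requirement. |
| Urine pregnancy test | Not relevant. |
| Breath alcohol 0.000 | No. It does not address cannabis. |
| CO below about 15 ppm | Not directed at it. The check is described as confirming abstinence from smoking. |
| Fasting since waking | No. It would bar THC eaten as food after waking, but not vaporizing. |

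That CO would miss vaporized THC is an inference. The Study Drug paragraph contrasts cigarettes, where "drug is lost through combustion and side stream smoke; a vaporizer is a closed system", with the vaporizer, but says nothing about CO detection.

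**2. Is the advised interval long enough?**

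Inputs from General Methods and Outpatient Methods: arrival about 9:00, discharge about 18:00, data collected for about 8 h after the marijuana dose, peak subjective effects up to 3 h, effects described as minimal at 8 h.

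- Dose time: 18:00 − 8 h = about 10:00.
- If the session day means the calendar day, non-use runs from midnight: 9 h to arrival and 10 h to dosing.
- Start of the 3 h window before dosing: 10:00 − 3 h = 7:00. Start of the 8 h window: 10:00 − 8 h = 2:00. Both fall after midnight, inside the advised period.

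The length is adequate. What is missing is a requirement, a check and a consequence.

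**3. The other safeguards**

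- The baseline battery (General Methods), including a baseline drive, comes before dosing, but no result is tied to a decision to stop.
- Continuous staff observation during sessions (Records, Privacy, and Confidentiality) has no stated start criterion.
- The dosing hold is triggered by signs or symptoms, not by recent use. The Risks section lists raised heart rate, red eyes and slurred speech among marijuana effects, so the hold would plausibly catch visible intoxication.

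Together these probably stop a participant who is evidently intoxicated. They do not stop one without obvious signs.

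**4. Where the protocol already applies such a rule**

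| Point | Sobriety or intoxication rule |
|---|---|
| Consent | Stated: return when sober |
| Session start, before dosing | None stated for cannabis beyond the CO check |
| Discharge | Stated: field sobriety test and report of no acute intoxication |

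**5. Number of occasions**

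- Session starts: 24 completers × 5 = 120.
- Active THC sessions: 24 × 3 = 72. Active alcohol sessions: 24 × 1 = 24. Active in total: 72 + 24 = 96.
- Alcohol dose in women: 0.8 × (1 − 0.15) = 0.68 g/kg.

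These are counts of sessions, not of risk. The documents give no rate of undisclosed use.

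**The case against.** The strongest reply is that the protocol largely handles this already. Participants are told not to use drugs before the session, smoking is gated by CO, food is barred, a baseline battery is run, staff observe throughout, and study drug is withheld for contraindicating signs. For a concern that is only about safety, signs are arguably what matter. This stands for visible intoxication and narrows the point to use without obvious signs.

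A second reply is that the remedy fits covert use poorly: someone who ignored the advice, looks well and does not disclose could pass a self-report and a sobriety test. This stands in part. A direct, recorded question and a stated consequence would still catch participants who answer honestly, and the sobriety test would catch some whose signs are not obvious.

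Third, the protocol elsewhere uses smoking terms for its own vaporized dosing, so the CO sentence may be meant to cover vaporizing. That is fair as to wording. The check would still be CO, and the documents do not say that CO detects vaporized use.

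Fourth, the consequences are limited. The Risks section describes marijuana as having low acute toxicity, participants know its effects, and they are observed, held until they pass the sobriety test, and not allowed to drive themselves home. This stands, and it is why the point is rated minor.

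A reader might also infer that the protocol breaks its own statement that "Active marijuana and active alcohol doses will not be administered in combination" (Study Design). It does not: that sentence governs what the study administers, and a participant's undisclosed earlier use does not contradict it.

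**Conclusion.** The point holds as a small safety gap. Cannabis has no required abstinence interval, the one marijuana-specific start check is a CO cut-off worded for smoking, and the wider session-day instruction is advice with no bearing on whether the session starts. The remaining exposure is recent non-smoked use without obvious signs.

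Its frequency is unknown. Any probability attached to the 96 active sessions would only restate an assumed rate, so none is given.

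Three stronger readings are not supported:

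- **That the advised period is too short.** From midnight it exceeds both the 3 h peak window and the 8 h figure, so no separate hour limit is needed at a 9:00 arrival.
- **That the comparison of conditions is biased.** Order is randomized and dosing is double-blind, and nothing in the documents ties prior use to a particular condition.
- **That daily users make this a large problem.** Study Population admits everyday users, but Data and Safety Monitoring describes use on at most 3 days a week. That discrepancy is a separate matter and is not relied on here.

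The conclusion assumes that the session day means the calendar day and that CO does not register vaporized THC. It also assumes that the attachments and consent forms, which were not available, contain no further session-day check.

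**What to change.** In Outpatient Methods:

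1. Add cannabis to the required abstinence list: no use by any route on the session day, counted from midnight, as a condition for starting.
2. At each session start, ask for and record the time, route and amount of last cannabis use.
3. Before the baseline battery, apply the two checks already used at discharge: the field sobriety test and a report of no acute intoxication.
4. Reschedule any session that fails, as the consent procedure already does for volunteers who are not sober.
5. Keep the CO cut-off, described as a check on recent smoking only.

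The cost is protocol wording, a few minutes per session using a test that staff already run, and an occasional rescheduled session. The added checks rest on self-report and behavior, not on an objective measure of THC, so they lower the chance of undetected use without removing it.

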Data Safety and Monitoring Plan: Data will be collected using a computerized data collection and management system wherever possible. This system automates the collection of data, which ensures the accuracy and completeness of data collection. The data are stored in a unique file on the hard drive of the computer and are printed after all the tasks are completed. In all instances, the data files do not contain the name of the subject; but instead, a unique eight-digit number identifies each subject. A computer file linking the unique number with the subject's name will be kept on a stand-alone, password-protected encrypted computer. All data requiring hand entry (e.g., urinalysis results) will be double entered by two separate staff members and comparison macros conducted to ensure accuracy. Data files for experimental tasks and physiological measures from each experimental session will be manipulated and combined into a single electronic spreadsheet for each subject by the statistician. Data for all volunteers will then be combined into a single electronic spreadsheet and separated by experimental measure for statistical analysis. The primary outcome measures will include driving performance on key measures (e.g., SDLP, brake latency, reaction time, collisions). Secondary outcomes will include observer ratings, safety outcomes (side effects and physiological measures) and cognitive/psychomotor performance; sex differences will be explored. Data will be analyzed using LMM for repeated measures designs along with other statistical analyses. The alpha level will be set at 5%. As noted above, wherever possible, data are collected using an automated computer system, which increases the accuracy and completeness of data collection and ensures the validity and integrity of the data. The initial data manipulation described above will be conducted twice and compared. All analyses are conducted by our statistician ([name]). The quality of manipulated data and data analyses will be monitored by random inspection by the PI and/or Co-Investigators.

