Study Title: Marijuana Effects on Simulated Driving Performance

Institution/Site:	University of Kentucky
Document (Approval/Update) Date:	IRB 12/26/23
NCT Number:	NCT03699540
IRB Number	43636
Coversheet created:	4/29/24

Statistical Analysis Plan

All analyses will be conducted using SAS Version 9.3 or higher (SAS Institute, Inc; Cary, NC, USA), and all hypothesis testing will be two-sided with a significance level of 0.05. P-values will be presented with 3 decimals and p-values that are less than 0.001 will be represented as <0.001.

Continuous data will be summarized using descriptive statistics: number of observations (n), arithmetic mean, standard error, minimum, and maximum. Frequencies and percentages will be used to summarize categorical (discrete) outcomes. Means and standard errors will be presented to two decimal places.

Demographics and Other Baseline Characteristics

Demographic and baseline characteristics will be summarized; no statistical comparisons will be made on demographic or baseline characteristics. The demographic and baseline characteristics will consist of age, sex, race, ethnicity, height (cm), weight (kg), and BMI (kg/m²).

Continuous variables (age, height, weight, BMI) will be summarized by n, mean, standard deviation, min, median, and max. Frequencies and percentages will be used to describe categorical (discrete) variables including gender, race, and ethnicity.

Analysis of Primary Outcomes

The primary Emax for Standard Deviation in Lane Position (SDLP: amount of weaving/swerving of the car in and out of the lane) and will be analyzed in a mixed model including the nine drug conditions with a compound symmetry covariance structure. Within each model, subject will be treated as random effects, and the remaining parameter as fixed effects. Mixed models are suited for data with repeated measures, correlations among observations within an individual subject, and the presence of missing data. The response of individual subjects is first modeled, and then the estimates for each individual are combined in a group analysis (Singer, 1998; Ballinger 2004; Diggle et al. 1996; Gibbons et al. 1993; Kreft and De Leeuw 1998). Tukey post-hoc tests will compare active doses to placebo and other relevant active dose comparisons.

Analysis of Secondary Outcomes

Secondary outcomes will include:

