- Raw time course data on driving performance (e.g., SDLP, number of lane changes, speed, number of collisions), driving VAS (e.g., driving difficult, drive

safely), drug VAS items (e.g., High, Good Drug Effects, Bad Drug Effects), subjective alcohol adjectives, mood scale, street value, observer adjectives, DSST, circular lights, heart rate, systolic blood pressure, diastolic blood pressure, respiration rate, and oxygen saturation from the nine dose conditions.

- Emax and Emin (where appropriate) on driving performance, drug VAS items, subjective alcohol adjectives, mood scale, street value, observer adjectives, DSST, circular lights, heart rate, systolic blood pressure, diastolic blood pressure, respiration rate, and oxygen saturation from the nine dose conditions.
- Secondary analyses will be completed in mixed models that include drug condition and time (when appropriate with an autoregressive covariance structure) with a compound symmetry covariance structure. Subject will be treated as random effects and the remaining parameters fixed. Tukey post-hoc tests will compare active doses to placebo and other relevant active dose comparisons.

Safety and Tolerability Analyses

Adverse events (AEs) recorded after signing informed consent but prior to the first dose will be recorded as baseline AEs and will be listed by subject but will not be included in the summary safety analysis. AEs will be summarized by relationship to study drug and severity.

Missing Data

Within-session missing data are expected to be less than 3% for each outcome. Inspection of missing data and correlates of missingness will be examined upon study completion. The use of mixed models as an analytic strategy obviates the need for the missing values to be imputed.

Identification and Summary of Protocol Deviations

Major protocol deviations from the participant's entry criteria through study completion will be documented and summarized as far as they can be extracted from the numeric and coded study data.

References:

Ballinger GA (2004) Using generalized estimating equations for longitudinal data analysis. *Organizational Research Methods* 7(2): 127-150.

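### The protocol's primary outcome is an open list of driving measures; the SAP's is SDLP Emax alone, and nothing says which governs

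*Protocol*

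**What the plan says.** **Protocol, Data and Safety Monitoring.** "The primary outcome measures will include driving performance on key measures (e.g., SDLP, brake latency, reaction time, collisions"). The same paragraph fixes the significance level: "The alpha level will be set at 5" per cent. Its secondary list covers observer ratings, safety outcomes and cognitive/psychomotor performance, and contains no driving measure. No summary statistic or time point is given, although under General Methods "Driving simulation will be tested at six time points during each test session".

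**Protocol, Objectives.** The primary aim refers only to simulated driving performance. Outpatient Methods gives lateral position variability and tactical measures as examples and leaves room for others.

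**SAP, opening paragraph.** "all hypothesis testing will be two-sided with a significance level of 0.05".

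**SAP, Analysis of Primary Outcomes.** This section opens as follows: "The primary Emax for Standard Deviation in Lane Position (SDLP: amount of weaving/swerving of the car in and out of the lane) and will". It then specifies a mixed model. The sentence appears to have lost a word and the heading is plural, but no other variable is named. On multiplicity: "Tukey post-hoc tests will compare active doses to placebo and other relevant active dose comparisons".

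**SAP, Analysis of Secondary Outcomes.** The first item is "Raw time course data on driving performance (e.g., SDLP, number of lane changes, speed, number of collisions"). The second is "Emax and Emin (where appropriate) on driving performance", with no exclusion of SDLP. Brake latency and reaction time do not appear by name anywhere in the SAP.

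**The concern.** The two documents give different answers to the question of which result carries the trial's primary claim. Suppose SDLP shows nothing and collisions, brake latency or reaction time reach significance. Under the protocol that is a primary finding. Under the SAP it is a secondary one or, for the last two measures, a result on an outcome the plan does not name. With no statement of precedence, the choice could be made after the data are seen.

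The error rate is also undefined under the protocol's wording. Tukey adjusts comparisons between conditions within one outcome and does nothing across outcomes. Several primary measures at an undivided 5% level, without a rule for whether one or all must succeed, leave the overall false-positive rate unspecified. Because the list is open, it has no stated upper limit.

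**Working it through.** **Step 1. Set the classifications side by side.**

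| Measure | Protocol, Data and Safety Monitoring | SAP |
|---|---|---|
| SDLP | Primary, no summary statistic | Emax primary; raw time course secondary; Emax not excluded from the secondary Emax/Emin item |
| Collisions | Primary | Secondary |
| Brake latency | Primary | Not named |
| Reaction time | Primary | Not named |
| Other driving measures | Could be primary (open list) | Secondary |

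Only SDLP is primary in both, and only the SAP says how it is summarised.

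**Step 2. Reproduce the stated level.** One primary outcome with one overall test at α = 0.05 has a false-positive rate of 1 − (1 − 0.05)^1 = 0.05. This is the SAP's position and it matches both documents.

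**Step 3. Four measures, one test each, any one sufficing.** The count of four and the 5% level come from the documents. The any-one rule and the correlations are assumptions.

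- Independent: 1 − 0.95^4 = 1 − 0.8145 = 0.1855.
- Upper bound for any dependence: 4 × 0.05 = 0.20.
- For a common correlation r among the four test statistics, each is Z_j = √r·C + √(1 − r)·E_j, where C and the E_j are independent standard normal. The error rate is P(at least one |Z_j| > 1.96).

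| r | P(at least one false positive) |
|---|---|
| 0 | 18.5% |
| 0.3 | 17.4% |
| 0.5 | 15.6% |
| 0.7 | 13.0% |

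**Step 4. The same question with the planned Tukey comparisons.** This was simulated under the global null with 24 completers (the protocol's goal), a complete crossover, compound symmetry, normal data and all pairs compared. A measure counts as a false positive if any pair is significant. The error degrees of freedom are 23 × (c − 1) for c conditions: 23 × 4 = 92 for the protocol's five sessions, and 23 × 8 = 184 for the nine conditions the SAP mentions. That difference in condition count is a separate inconsistency; both are shown so that the answer does not depend on it.

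| r | Five conditions | Nine conditions |
|---|---|---|
| 0 | 18.4% | 18.7% |
| 0.3 | 17.8% | 18.1% |
| 0.5 | 16.6% | 16.6% |
| 0.7 | 14.0% | 14.3% |

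Repeat runs differ by up to about half a percentage point. For one measure alone the rate is 5%, so Tukey does its job within an outcome. The excess comes entirely from having four.

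**Step 5. Effect of a split.** Bonferroni gives 0.05 / 4 = 0.0125 per measure. With one independent test each, 1 − 0.9875^4 = 0.049. With five-condition Tukey at 0.0125 per measure, the simulated rate is about 4% to 5% over the same correlations.

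**The case against.** The best reply is that the SAP narrows the protocol rather than contradicting it. The protocol sentence sits in a data-handling narrative in an IRB form and offers examples. The SAP is the dedicated analysis document and names one variable with one summary statistic. SDLP heads the protocol's list, and the Background section says lateral control measures appear most sensitive to marijuana. The Dose Selection section calls the study small-scale and exploratory, and no sample size or success rule depends on the choice. The inflation figures describe an any-one-suffices rule that neither document adopts, apply Tukey to the protocol's list although the protocol does not mention it, and assume normality for collision counts.

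Much of this is fair on size. The figures are conditional, and the excess is nil if the SAP governs. Some details are minor: the faulty grammar may be a slip or a text-extraction loss, the Emax overlap is a matter of tidying, and brake latency and reaction time could enter through the SAP's own open-ended secondary list. The dates do not show that any outcome was chosen after data were seen.

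The central point stands. Neither document says the SAP narrows the protocol. The protocol has no driving measure in its secondary tier, and collisions are primary in one text and secondary in the other. An exploratory label does not reconcile them when both use primary and secondary tiers and a 5% level.

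**Conclusion.** The concern holds and should be fixed before results are interpreted. The two documents disagree on what can carry the primary claim, and the protocol's version is not closed.

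The false-positive rate across primary outcomes is 5% under the SAP. Under the protocol's list it is about 13% to 18.5% with one test per measure, or about 14% to 19% with the planned Tukey comparisons. These ranges assume exactly four measures, success on any one, a common correlation between 0 and 0.7, and normal data; the Tukey figures also assume 24 completers. If further measures were added under the open list, the rate could not be bounded. The finding itself rests on the conflict in wording and does not depend on these figures.

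**What to change.** 1. State SDLP Emax as the single primary outcome in identical words in the protocol's Data and Safety Monitoring section and the SAP's Analysis of Primary Outcomes. Repair the SAP sentence and remove the open-ended wording from the protocol.
2. Move brake latency, reaction time and collisions to the protocol's secondary list. Add brake latency and reaction time by name to the SAP's secondary list; number of collisions is already there.
3. Limit the SAP's secondary Emax/Emin item to driving measures other than SDLP Emax.
4. Date the change and state whether it was made before unblinding. The SAP coversheet carries an IRB approval/update date of 12/26/23 and the protocol anticipates ending on 4/1/2025; neither document says whether outcome data had been seen.

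If several measures must stay primary, close the list, give the summary statistic for each and state the rule: Holm or Bonferroni (0.0125 each for four) if any one suffices, or no split if all must be significant. Collision counts would also need a check that the planned normal-theory model suits them.

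The cost is a few sentences of editing and a dated rationale. The drawback of the single-primary option is that the three demoted measures can no longer support a primary claim.
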